## Data Analysis Plan

The purpose of the study is to measure any differences in the two study arms. Thus, t-test will be performed. Descriptive statistics will be utilized to identify the normality of the data.

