## **Outcomes**

Outcomes will be collected at the start of the study, at the start of each therapy session, and during one-week post-therapy follow-up.

This study is a two arm, prospective randomized investigation to examine the impact of PhoRTE and EMST on VHI-10, AVI, acoustic, aerodynamic, and auditory-perceptual outcomes collected pre-(baseline) and post-intervention (short-term follow-up).

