### *VHI-10*

The primary outcome is the Voice Handicap Index-10 (VHI-10) score. The VHI-10 is a patient-centered outcome that quantifies a patient's perception of handicap caused by a voice disorder and will be measured at every session. VHI-10 will be anchored to baseline VHI-10 score (each item anchored) for the 1 week follow-up (will be administered without anchoring). Secondary outcomes include the following:

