### *Participants*

N=28 male and female participants diagnosed with vocal fold atrophy. 14 patients will be recruited for each arm of the study.

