**Intervention/Experimental Protocol**

*Outline Of Procedures*

The experimental protocol consists of pre-treatment and post-treatment acoustic and aerodynamic data collection and four 45-minute sessions of voice therapy. All subjects will complete PhoRTE therapy, and those in the EMST+PhoRTE arm in the study will also undergo EMST training. Before each PhoRTE therapy, subjects will report to the PI so that therapists are blinded as to which treatment group each subject is in.

Baseline	Therapy 1	Therapy 2	Therapy 3	Therapy 4	Post-Tx
Pre-Tx Acoustic and Aerodynamic Measurements, VHI-10, AVI, MEP	PhoRTE +/- EMST  VHI-10 MEP	PhoRTE +/- EMST  VHI-10 MEP	PhoRTE +/- EMST  VHI-10 MEP	PhoRTE +/- EMST  VHI-10 MEP	Acoustic and Aerodynamic Measurements, VHI-10, AVI, MEP

*PhoRTE Therapy (Standard of Care Treatment)*

Each therapy session will last for 45 minutes.

1st PhoRTE treatment session

- Check in with your patient about current status
  - o Do you have any questions since we last met? Do you have any concerns about your ability to commit to PhoRTE?
- Check in with the patient to verify implementation of voice care program
  - o Dehydration, non-phonatory inflammation (reflux, illness)
  - o Phonotrauma (throat clearing, cough)
  - o Caffeine
- Provide patients with PhoRTE therapy information sheets, phrase list, and practice sheets
- Set up the patient for home practice
  - o Verify that patient is able to download a decibel meter app successfully, and configure the app’s settings with a sound pressure level meter for home practice

- Orient the patient to the app; teach them how to open and utilize the app for home practice; demonstrate for the patient how to standardize mic-to-mouth distance
- Verify that 10 functional phrases for practice are written. Review phrases for length and that they are representative of typical communication
- Teaching proper breathing form
  - Establish efficient respiratory mechanisms to effectively execute PhoRTE exercises
  - Ex. "Place your hand on your upper abdomen just above your belly button. Now, I want you to sustain the sound "sh" for as long as is comfortable. Notice the inward movement of your hand as you exhale and sustain "sh." Let's practice this breathing a few more times until you feel comfortable with this task."

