### *Auditory Perceptual Analysis*

3 blinded raters (tbd) will listen to the sentence “we were away a year ago” and rate on 100mm VAS in REDCap. The initial and final evaluations will be rated, for a total of 2 samples per participant x 28 participants = 56 samples.

Raters will be paid \$20/hour for ratings. Ratings should take in total 2 hour-long sessions.

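### The t-test plan names no tested variable and no baseline adjustment, although every efficacy outcome has a baseline value

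*Combined protocol and SAP*

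**What the plan says.** The Data Analysis Plan is three sentences long. It gives the aim ("The purpose of the study is to measure any differences in the two study arms"), the method ("Thus, t-test will be performed") and a descriptive check of normality. It does not state the outcome, the time point, whether the test is two-sample or paired, whether the tested value is a follow-up score or a change, or any covariate.

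Elsewhere the documents show that baselines are collected:

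- The Outcomes section describes "outcomes collected pre-(baseline) and post-intervention (short-term follow-up") for VHI-10, AVI, acoustic, aerodynamic and auditory-perceptual outcomes.
- The schedule under Outline Of Procedures lists "Pre-Tx Acoustic and Aerodynamic Measurements, VHI-10, AVI, MEP" at the baseline visit, and the same measures after treatment.
- Under Auditory Perceptual Analysis, "The initial and final evaluations will be rated" by blinded raters.

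The VHI-10 section makes the VHI-10 score primary but does not define a change. The Participants section sets the size: "14 patients will be recruited for each arm of the study".

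**The concern.** Two things follow from the missing detail.

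First, the test is not defined. A follow-up-score t-test and a change-score t-test are different analyses and can disagree. With the wording as it stands, the choice could be made after the data are seen.

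Second, both candidate tests are usually less precise than a baseline-adjusted model. The follow-up test ignores the baseline. The change test subtracts it in full, which over-corrects unless the correlation is high. Each leaves part of any chance baseline difference in the estimate. With 14 per arm such differences are common, and the analysis is the cheapest place to gain precision.

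**Working it through.** **Inputs from the documents.** N = 28, 14 per arm (Participants); a t-test (Data Analysis Plan). The documents give no power calculation, so there is no stated figure to reproduce beyond 2 × 14 = 28.

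**Assumptions, none of them in the documents.** Two-sided alpha 0.05; superiority comparison; true difference 0.8 SD; equal SDs at both time points; linear relation with a common slope; complete data; baseline-to-follow-up correlation ρ varied from 0 to 0.9.

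**Variance of the arm difference**, in units of 2·SD²/14:

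- follow-up score: 1
- change score: 2(1 − ρ)
- ANCOVA: (1 − ρ²) × (N − 3)/(N − 4) = (1 − ρ²) × 25/24, where 25/24 = 1.042 is the average cost of estimating the slope

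**Break-even points.**

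- Against follow-up: (1 − ρ²) × 25/24 = 1, so ρ² = 1/25 and ρ = 0.20.
- Against change: (1 + ρ) × 25/24 = 2, so ρ = 0.92.

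Counting the lost degree of freedom in the critical value moves the range slightly, to 0.21–0.91. With 12 or 10 analysed per arm, the variance range is 0.22–0.90 or 0.24–0.88.

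**Power for a 0.8 SD difference** (noncentral t; 26 df for the t-tests; 25 df for ANCOVA, averaged over the chance baseline gap):

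| ρ | Follow-up | Change | ANCOVA |
|---|---|---|---|
| 0 | 53% | 30% | 51% |
| 0.2 | 53% | 36% | 53% |
| 0.3 | 53% | 41% | 55% |
| 0.5 | 53% | 53% | 63% |
| 0.7 | 53% | 75% | 80% |
| 0.8 | 53% | 90% | 91% |
| 0.9 | 53% | 99.5% | 99.5% |

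Simulation agrees with these values, and unconditional type I error is about 5% for all three methods. At a smaller assumed effect of 0.5 SD and ρ = 0.5, power is 25% for either t-test and 30% for ANCOVA.

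**Precision at ρ = 0.5.**

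- Follow-up (or change) 95% CI half-width: 2.056 × √(2/14) = 0.78 SD.
- ANCOVA: 2.060 × √(2/14 × 0.75 × 25/24) = 0.69 SD.
- The difference detectable with 80% power falls from 1.10 to 0.97 SD.

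**Chance baseline imbalance.** The baseline gap between arms has standard error √(2/14) = 0.378 SD. So P(|gap| > 0.5 SD) = 2 × [1 − Φ(0.5/0.378)] = 0.186, about 19%. With a 0.5 SD gap and ρ = 0.5, the follow-up estimate shifts by ρ × 0.5 = +0.25 SD and the change estimate by (ρ − 1) × 0.5 = −0.25 SD. Given that gap, type I error is about 6.5% (follow-up) and 6.6% (change), against 4.9% for ANCOVA.

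**The open choice.** If whichever of the two t-tests reached significance could be reported, simulated type I error would be about 9% for ρ between 0.3 and 0.7. This measures what the wording permits. It does not suggest that anyone intends it.

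**The case against.** The best case against the point is that a randomised t-test is valid, so preferring ANCOVA corrects no error; only the unstated variable is a defect, and naming either t-test would cure that. This is right about validity, and right that any prespecified choice closes the post-hoc option. It does not remove the efficiency argument. With ρ unknown, the sponsor cannot tell which t-test is the weak one, and a wrong pick can cost over 20 power points (change score at ρ = 0, follow-up score at ρ = 0.7). ANCOVA loses at most about 2 points to the better of the two.

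A second objection is that the text leans towards change: the Abstract speaks of outcomes before and after treatment, and the AVI section sets baseline beside the 1-week follow-up. If change is meant, the ANCOVA gain at 0.8 SD is 10 points at ρ = 0.5, 5 at 0.7, under 2 at 0.8 and none at 0.9. That stands as a limit on the size of the gain, but these hints do not define the test.

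Other limits also stand. The 0.2 and 0.9 bounds are break-even points, so gains near them are negligible. At smaller effects the trial stays underpowered whichever method is used. The four session VHI-10 values go unused in the simple model; a repeated-measures analysis would be an alternative. Linearity deserves a look for the number of breaths, and for VHI-10 because entry at a score of 1 admits near-floor baselines. The conditional error rates describe one chosen gap; averaged over randomisations each test holds 5%.

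**Conclusion.** The concern holds. No section names the tested variable or a baseline covariate, and all the efficacy outcomes have the baseline needed for adjustment. At 14 per arm, ANCOVA matches or beats both t-tests for correlations from about 0.20 to 0.92, with a worthwhile gain at roughly 0.4 to 0.8. At an assumed 0.8 SD effect that gain over the better t-test is 10 points at 0.5 and 5 at 0.7.

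The sizes rest on the unstated correlation and effect, equal SDs, linearity and complete data. They apply to a superiority comparison only. The trial remains valid without the change, so this is a recommended improvement and not a condition for going ahead.

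**What to change.** Replace the t-test sentence with wording such as: *The primary analysis is a linear model of 1-week VHI-10 on study arm and baseline VHI-10, reporting the adjusted difference between arms with its 95% confidence interval; each secondary outcome uses the same model with its own baseline value.* Add a line on checking linearity and on what will be done if it fails. A site term is optional.

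The VHI-10 section must also be reconciled. It says the 1-week score is anchored to the baseline item scores and, in the same sentence, "will be administered without anchoring". Anchoring could change the correlation, and with it the gain from adjustment.

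The adjusted interval serves either the added-benefit aim in the Objective or the at-least-as-effective hypothesis in the Background.

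Cost: one sentence or two and no new data; one degree of freedom; about 4% variance inflation (25/24), which is at most about 2 power points if the correlation is near 0; and a linearity assumption. A site term that explains nothing would cost roughly 1 to 2 further points.

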#### *EMST Training (Study procedure)*

The EMST device will be used to incrementally strengthen the respiratory muscles each week. The device will be calibrated each week using a manometer. Maximum expiratory pressure (MEP) will be measured before beginning each therapy session, and this will be used to calibrate the device for the weekly exercises. The device will be set to 75% of MEP for the week’s exercises.

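### The efficacy analysis is an unspecified t-test; a baseline-adjusted model of one-week VHI-10 that also uses the session scores would be more precise and would cope better with missed follow-up visits

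*Combined protocol and SAP*

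**What the plan says.** The VHI-10 section states: "The primary outcome is the Voice Handicap Index-10 (VHI-10) score", and adds that it "will be measured at every session". The Outcomes section agrees on timing: "Outcomes will be collected at the start of the study, at the start of each therapy session", and again at the one-week follow-up. In the schedule table under Intervention/Experimental Protocol, the baseline column reads "Pre-Tx Acoustic and Aerodynamic Measurements, VHI-10, AVI, MEP", each of the four therapy columns reads "PhoRTE +/- EMST VHI-10 MEP", and the post-treatment column again includes VHI-10 and MEP. That makes six planned values of each measure per participant. The plus-or-minus sign shows that both arms are covered, and the Data Entry section does not restrict either measure by arm.

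On sample size, the Participants section says "14 patients will be recruited for each arm of the study".

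The Data Analysis Plan gives the purpose as measuring differences between the two arms and continues: "Thus, t-test will be performed". It adds only descriptive statistics to look at normality. It does not say which variable is tested, at which visit, as a score or a change, in whom, or what happens when a value is missing. The nearest guide is the Outcomes section, which describes the comparison, VHI-10 included, as baseline against short-term follow-up.

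For MEP, the EMST Training section says "Maximum expiratory pressure (MEP) will be measured before beginning each therapy session" and uses the value to calibrate the device. Data Entry lists MEP among the outcomes completed at each session. It is not among the primary and secondary outcomes described under Outcomes, and the Data Analysis Plan names no comparison for it.

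**The concern.** A two-sample t-test takes one number per person. If that number is the one-week score, baseline VHI-10 plays no part, although it is likely to be the best single predictor of the outcome. If it is the change from baseline, baseline is used with a fixed coefficient of one, which is less efficient than letting the data estimate the coefficient. Either way, the four session scores do not enter the comparison, and a participant without a one-week score contributes nothing to it.

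With 14 per arm, precision is scarce and each lost participant counts. If those who leave are the ones not improving, and they leave one arm more than the other, a completer comparison can also be biased. The session scores hold some of the information needed to correct for that.

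MEP matters because the Background rests the case for EMST on stronger expiratory muscles. Without a planned comparison of MEP between arms, a null VHI-10 result could not separate a device that failed to strengthen from strength that failed to help the voice.

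**Working it through.** **What the t-test uses.** Planned VHI-10 values: 28 × 6 = 168. A t-test on the one-week score uses 28 of them. A t-test on change uses 28 × 2 = 56 and leaves 28 × 4 = 112 unused. Because VHI-10 is taken at the start of each session, the Therapy 1 score precedes any treatment, so only Therapy 2, 3 and 4 give on-treatment session scores.

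**The plan's own figure.** No alpha, power, SD, effect size or dropout rate supports N = 28, so it cannot be reproduced. Assuming two-sided alpha 0.05 and 80% power, the exact t calculation gives a detectable difference of 1.10 SD with 14 per arm.

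**Assumptions for the rest (none is in the documents).** SD 7; covariance between visits 49 × (0.55 + 0.45 × 0.6^lag); true arm difference −3 at one week; 14 per arm.

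**Complete data.** Baseline and one week are five visits apart, so the correlation is r = 0.55 + 0.45 × 0.6^5 = 0.585 and r² = 0.342.

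- t-test on one-week score: SE = 7 × √(2/14) = 2.65
- t-test on change: SE = 7 × √(2(1 − 0.585) × 2/14) = 2.41
- ANCOVA: SE = 7 × √((1 − 0.342) × 2/14) = 2.15, or 2.19 after the small-sample factor √(1 + 1/24) for estimating the baseline slope

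Simulation gave 2.63, 2.39 and 2.18, in line with the formulas. The longitudinal estimate also gave 2.18, so with complete data the session scores add nothing to the one-week contrast. Baseline adjustment cuts the SE by 1 − 2.18/2.63 = 17% against the post score and by 1 − 2.18/2.39 = 9% against change.

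**20% of final visits missing at random, after session 4.** Simulated SEs:

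| Analysis | SE |
|---|---|
| t-test on one-week score | 3.00 |
| t-test on change | 2.74 |
| ANCOVA, completers | 2.51 |
| Longitudinal | 2.35 |

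Session scores therefore cut the SE by 1 − 2.35/2.51 = 6%. When the 20% left at random after Therapy 2 instead, the figures were 2.55 (ANCOVA) and 2.52 (longitudinal), almost no gain.

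**Sensitivity to the correlation pattern.** A separate calculation used known covariance, with correlations from 0.5 to 0.9. If 3 of 14 per arm miss only the final visit, 11 are observed. The six-visit model has an effective 11.5 to 11.9 per arm under compound symmetry and 11.6 to 13.0 under AR(1). It recovers part of the loss, not all of it.

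**Bias, 20% missing, true effect −3.**

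| Who misses the one-week visit | Change t-test | ANCOVA | Longitudinal |
|---|---|---|---|
| EMST non-improvers only, by observed scores | −4.19 | −3.87 | −2.94 |
| The same, stricter rule (worst change at session 4 always lost) | −4.73 | −4.32 | −3.00 |
| Non-improvers in both arms equally | −2.94 | −2.96 | −2.97 |
| EMST arm, by the unobserved one-week score | not given | not given | −3.93 |

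The longitudinal figures come from a likelihood estimate using baseline and session 4, not from a full repeated-measures fit with many covariance parameters.

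**The case against.** The strongest reply is that the Data Analysis Plan is merely brief. It never commits to a completer analysis, and a reader who infers that participants without a one-week visit will be lost is going beyond the text. That is correct: the loss follows from the natural reading together with the absence of a missing-data rule, and is not stated. But the plan also names no method that would use baseline or session scores, so a better method can be proposed whatever the sponsor had in mind.

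A second reply is that most of the precision gain comes from adjusting for baseline, so choosing a repeated-measures model over ANCOVA is close to preference. This largely stands. With complete data the two are equal, and the extra 6% needs late, random dropout.

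Third, a reader might infer from the first two rows of the bias table that the planned test will overstate benefit by some 40% (−4.19 against −3). The documents do not support that. They give no dropout rate or mechanism, and half of the participant payment ($50 of $100) is held for the one-week visit, which favours retention. The bias disappears if non-improvers leave both arms equally. Where dropout depends on the unobserved score, the longitudinal estimate is itself about 31% too large (0.93/3).

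Fourth, a five-visit unstructured covariance has 15 parameters, which is many for 28 people, and its behaviour at this size has not been shown. That stands, and it argues for a simpler structure.

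Two further overstatements should be avoided. The session data are not discarded: session MEP calibrates the device, and a VHI-10 increase is part of the safety rule. Nor is MEP missing from every outcome list, because Data Entry includes it.

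**Conclusion.** The point holds as a recommendation to replace an unspecified t-test with a better and equally feasible analysis. The main, dependable gain is baseline adjustment: an SE of about 2.18 against 2.63 or 2.39 with complete data, under an assumed SD of 7 and a baseline-to-follow-up correlation of 0.585. A stronger correlation would enlarge the gain over the post-score test and shrink the gain over change.

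The session scores are of secondary value. They give around 6% when 20% of final visits are lost at random after session 4, less with earlier dropout, and protection from bias only where dropout depends on scores already observed.

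The documents do not establish that the planned test will be biased, nor that the session scores would raise power with full follow-up.

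For MEP, the gap is that it is collected as an outcome but not ranked among the outcomes or given a comparison.

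**What to change.** Rewrite the Data Analysis Plan along these lines.

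- **Primary estimate:** the arm difference in VHI-10 at the one-week visit, adjusted for baseline VHI-10 and for site (two institutions recruit), in all randomised participants as assigned.
- **Model:** a likelihood-based repeated-measures model that includes the session scores, so that participants missing the one-week visit still contribute. Use a parsimonious covariance suited to 28 participants, and name baseline-adjusted ANCOVA as the fallback.
- **Therapy 1 score:** treat it as pre-treatment.
- **Missing data:** state the assumption that missingness depends on observed scores, and say plainly that bias from dropout depending on unobserved scores would remain.
- **Anchoring, to be settled first:** the VHI-10 section says both that the one-week score is anchored to baseline and that it is administered without anchoring. These statements must be reconciled before session and follow-up scores share a model.
- **MEP:** name it as a mechanistic secondary outcome and compare it between arms with the same baseline-adjusted model.

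The cost is revised wording, slightly more programming, and more modelling assumptions than a t-test at a small sample size. No visit or measurement is added. The change should be made before results are seen.

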## Summary

The results from this study will allow the clinicians to improve patient outcomes. Hopefully, this study will be a precursor to future studies, aimed at treating Presbyphonia.

